6.6.5 Early Termination Assessment

Participants that discontinue the study early due to COVID-19 infection or are hospitalized for any reason are encouraged to attend the early termination assessment to the best of their ability. If the participant is unable to complete the treatment diary or attend the early termination assessment, the designated emergency contact is encouraged to submit this information on behalf of the participant to the best of their ability.

Protocol deviations to be recorded for this study include visit/phone/telehealth procedure deviations and noncompliance; PRO noncompliance; study medication dosing noncompliance; and dispensing deviations. A special emphasis will be placed on dosing errors, lack of completion of the required daily PRO reporting, and the incomplete return of study medication at the conclusion of the study.

Study medication noncompliance is defined as less than 80% of expected doses administered while on possible study treatment. PRO noncompliance is defined as less than 70% of possible reporting days of data recorded, eg. before a hospitalization, or an early termination.

7 ADVERSE EVENTS ASSESSMENTS

7.1 Adverse Event Definition

As per Good clinical Practice (GCP) guidelines, an AE is any untoward medical occurrence in a patient or clinical investigation participant administered a pharmaceutical product and which does not necessarily have to have a causal relationship with this treatment. An AE can therefore be any unfavorable and unintended sign (including an abnormal laboratory finding), symptom, or disease temporally associated with the use of a medicinal (investigational) product, whether or not related to the medicinal (investigational) product.

AEs will include (1) any new medical condition (sign/symptom/disease) that occurs during the AE reporting period, or (2) any preexisting condition that worsens in severity or frequency or changes in character during the AE reporting period.

An SAE is defined as an AE that, in the view of either the Investigator or Sponsor, meets any of the following criteria:

- Results in death
- Is a life-threatening AE
 - A life-threatening AE is defined as an AE that in the view of either the Investigator or Sponsor, places the patient or participant at immediate risk of death. It does not include an AE that, had it occurred in a more severe form, might have caused death.
- Requires inpatient hospitalization or prolongation of existing hospitalization (except hospitalization for elective procedures for a pre-existing condition that has not worsened, admission to a nursing home or rehabilitation facility, or social admissions)
- Results in persistent or significant disability or incapacity (substantial disruption of the ability to conduct normal life functions; it does not include experiences of relatively minor medical significance such as uncomplicated headache, nausea, vomiting, diarrhea, influenza, or accidental trauma [eg, sprained ankle] that may interfere or prevent everyday life functions but do not constitute a substantial disruption)
- Is a congenital anomaly or birth defect (ie, an adverse outcome in a child or fetus of a female participant exposed to the study product)
- Important medical events that do not meet any of the above criteria may be considered serious when, based upon appropriate medical judgment, they jeopardize the participant and may require intervention to prevent one of the other outcomes listed in this definition

7.2 Method of Detecting AEs and SAEs

Recording, evaluating, and assessing causality of AE and SAE methods and the procedures for completing and transmitting SAE reports are provided in Section 11.

Care will be taken not to introduce bias when detecting AEs and/or SAEs. Open-ended and non-leading verbal questioning of the participant is the preferred method to inquire about AE occurrences.

7.3 Performing Adverse Events Assessments

The Investigator is responsible for monitoring of participants for AEs/SAEs over the assessment period as specified in the Schedule of Events (Table 4). Each AE/SAE will be evaluated as described in Section 7.4.1 and Section 7.4.3. Treatment of any AE/SAE will be managed by the participant's healthcare provider. If any aspect of evaluation or treatment of an AE/SAE is performed by a physician who is not part of the study team, the Investigator will ensure that the appropriate party is contacted as promptly as possible to collect the relevant information and documentation to complete the protocol-required assessment of each AE/SAE.

7.4 Timing

The Sponsor's medical monitor will have read-only access to the AEs recorded within the eCRF. All SAEs must be reported within 24 hours of disclosure/discovery. All SAEs will be recorded and reported to the Sponsor or designee immediately via automatic notification procedures from the eCRF and under no circumstance should this not exceed 24 hours. The Investigator will submit any updated SAE data to the Sponsor within 24 hours of it being available.

Adverse events and SAEs will be collected from the start of study treatment until the Follow-Up assessment as specified in the Schedule of Events (Table 4). Medical occurrences that begin before the start of study intervention but after obtaining informed consent will be recorded on the Medical History/Current Medical Conditions section of eCRF, not on the AE section.

Investigators are not obligated to actively seek AEs or SAEs after conclusion of the study participation. However, if the Investigator learns of any SAE, including a death, at any time after a participant has been discharged from the study, and he/she considers the event to be reasonably related to the study intervention or study participation, the Investigator must promptly notify the Sponsor.

7.4.1 Reportability

The Investigator, CRO medical monitor and Sponsor's medical monitor are responsible for determining whether an event should be classified as serious. If in the opinion of the Investigator, the AE meets the criteria of an SAE, the SAE is to be reported to the Sponsor or Sponsor's medical monitor designee. All SAEs, regardless of causality, must be reported. SAEs must be reported from the time the Informed Consent Form (ICF) is signed until 30 days after the last dose of study drug. SAEs considered related to study drug that occur after the specified Follow-up period should also be reported.

For expedited reporting purposes, SAEs assessed as Definitely Related, Probably Related or Possibly Related by the Investigator will be considered as "Related" events, while those assessed as Not Related will be considered as "Not related" events. These processes will be delineated in the CRO prepared, Safety/Medical Monitoring Plan, in consultation with sponsor's medical monitor prior to study.

7.4.2 Severity

The intensity (severity) of each AE will be assessed using the guidelines below:

- Mild: Does not interfere with usual activities, easily tolerated, requires no treatment.
- **Moderate**: Somewhat interferes with usual activities, may cause discomfort, may require treatment.
- **Severe**: Significantly interferes with usual daily activities, may be incapacitating, may require treatment.

Severity of an event is not the same as seriousness. Regardless of severity rating, an AE is considered serious if it meets the criteria for an SAE.

7.4.3 Relationship between Adverse Event and Study Drug

The relationship between the AE and study drugs (ie, separate assessments for relationship to study treatment) will be determined as one of the following:

- Definitely Related
- Probably Related
- Possibly Related
- Not Related

For analysis purposes, AEs assessed as Definitely Related, Probably Related or Possibly Related by the Investigator will be considered as "Related" events, while those Not Related will be considered as "Not related" events.

Causality will be determined based on clinical judgment and the following guidelines:

Definitely Related:

The event followed a reasonable temporal sequence from the time of study medication administration and/or followed a known response pattern to the study medication and could not have been produced by other factors such as the subject's clinical state, therapeutic intervention, or concomitant therapy and either occurred immediately following study medication administration or improved on stopping the medication.

Probably Related:

The event was reasonably temporally related to study medication administration, was consistent with known effects of the study medication, improved upon withdrawal of the study medication, and was unlikely explained by another etiology.

Possibly Related:

The event was reasonably temporally related to study medication administration which follows a known or expected pattern of the suspected medication but could be explained by another etiology.

Not Related:

The event was clearly due to extraneous causes (e.g., diseases, environment), which was to be specified if known; or the event was most likely produced by other factors such as the subject's clinical state, therapeutic interventions, or concomitant therapy and did not follow a known response pattern to the study medication.

The CRO Medical Monitor will review the Investigator's assessment of causality and may agree or disagree. Both the Investigator's and CRO Medical Monitor's assessments will be recorded. The CRO Medical Monitor will have the final say in determining the causality.

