7.4.5 Expectedness

An unexpected AE is one of a type not identified in nature, severity or frequency in the current Investigator's brochure. Expected events may include upper respiratory irritation-like symptoms due to use of the nasal spray.

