7.13 Study Stopping Rules

A formal plan for interim data monitoring for futility will be established. Review of serious, unexpected, and related AEs by the CRO Medical Monitor, Data Safety Monitoring Board (DSMB), IRB, or HC/ FDA or applicable relevant local/national regulatory authorities may also result in suspension of further study agent administration. Health Canada/FDA/IRB/or local/national regulatory authority and study Sponsor(s) retain the authority to suspend additional enrollment and study agent for the entire study, as applicable.

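### As worded, the Probably Related and Possibly Related grades in Section 7.4.3 require a known effect, so a reaction new in nature can fit no causality grade and its related/SUSAR label becomes unreliable

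*Combined protocol and SAP*

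**What the plan says.** Section 7.4.3 asks for one of four ratings, made with clinical judgment and a set of guidelines.

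- **Definitely Related:** reasonable timing "and/or followed a known response pattern to the study medication and could not have been produced by other factors", plus either immediate onset or improvement on stopping.
- **Probably Related:** reasonable timing, and the event "was consistent with known effects of the study medication, improved upon withdrawal of the study medication, and was unlikely explained by another etiology".
- **Possibly Related:** reasonable timing, for an event "which follows a known or expected pattern of the suspected medication but could be explained by another etiology".
- **Not Related:** clearly due to extraneous causes; or most likely due to other factors, where the event also "did not follow a known response pattern to the study medication".

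The first three grades are pooled as Related for analysis. Section 7.4.1 does the same for expedited reporting: "SAEs assessed as Definitely Related, Probably Related or Possibly Related by the Investigator will be considered as" related.

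Section 7.4.5 sets expectedness against the Investigator's brochure: "An unexpected AE is one of a type not identified in nature, severity or frequency". Section 7.6.1 defines a SUSAR as a serious drug reaction not identified in the risk information in those same respects. Section 7.13 names one adverse-event route to suspending study agent: "Review of serious, unexpected, and related AEs by the CRO Medical Monitor" and by the safety board, IRB or authorities.

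**The concern.** Relatedness in the two middle grades depends partly on the effect being already known. A SUSAR, and the event described in Section 7.13, must be both related and unexpected. For a reaction new in nature these two demands pull against each other. A serious event with plausible timing that resolves off drug has no natural place on the scale unless every other explanation is ruled out. The scale is also out of order: a new reaction can reach the top grade but neither of the two grades meant for weaker evidence.

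This trial is a likely place for a new reaction to appear. Up to 11,480 participants start treatment at 1:1, so about 11,480 / 2 = 5,740 would use NONS. The two earlier NONS trials described in Section 1.5 are much smaller: 103 participants received NONS in one, and the other had 79 participants across both arms. The brochure may hold further data.

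Investigators faced with the gap may resolve it differently, and some may choose Not Related. That would affect expedited and SUSAR classification (7.4.1, 7.6.1), the Section 7.13 trigger, and the relationship split in the safety tables (9.5.4). It would also affect SAE reporting after follow-up, which Sections 7.4 and 7.4.1 ask for only when the investigator considers the event related.

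**Working it through.** The plan gives no figure to reproduce here. The check takes the definitions in Section 7.4.3 literally and asks which grades an event can meet.

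**Inputs.** The event has a reasonable time relation to dosing. Four features vary: known pattern (yes/no), immediate onset (yes/no), improvement on stopping (yes/no), and strength of another cause at five levels (impossible, unlikely, could explain, most likely, clearly extraneous). The five levels are a reading of the wording; the protocol does not list them. Each pattern status has 2 × 2 × 5 = 20 combinations.

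**Rules.**
- Definitely: other cause impossible, and (immediate onset or improvement on stopping). A known pattern is optional because of the and/or.
- Probably: known pattern, improvement on stopping, and other cause at most unlikely.
- Possibly: known pattern, and other cause unlikely, able to explain, or most likely.
- Not Related: other cause clearly extraneous; or most likely with no known pattern.

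**Results** (four combinations per cell):

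| Other cause | Known pattern | No known pattern |
|---|---|---|
| Impossible | 3 related, 1 no grade | 3 Definitely, 1 no grade |
| Unlikely | 4 Possibly (2 also Probably) | 4 no grade |
| Could explain | 4 Possibly | 4 no grade |
| Most likely | 4 Possibly | 4 Not Related |
| Clearly extraneous | 4 Not Related | 4 Not Related |
| **Total of 20** | **15 related, 4 Not Related, 1 no grade** | **3 related, 8 Not Related, 9 no grade** |

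The two rows that matter are *unlikely* and *could explain*. Without a known pattern, 4 + 4 = 8 of 8 combinations fit no grade. With a known pattern, 8 of 8 fit Possibly or Probably Related. These are counts of logical cases, not probabilities.

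**Worked case.** A serious event of a kind not previously known starts on Day 3 and resolves off drug; another cause is unlikely but not excluded. It is not Definitely (other factors remain), not Probably (not a known effect), not Possibly (no known pattern) and not Not Related (other factors are not the most likely cause). It fits 0 of 4.

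**Scope.** Sections 7.4.5 and 7.6.1 count an event as unexpected if it differs in nature, severity or frequency. A known kind of reaction at a new severity or frequency still has a known pattern, so it can be both related and unexpected. The gap is confined to reactions new in nature.

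**The case against.** Several points on the other side stand.

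- **Guidelines, not rules.** The definitions are applied with clinical judgment. The 0-of-4 result describes the wording, not what every investigator would do.
- **Known pattern is not tied to the brochure.** Section 7.4.3 does not define known effects by the list used for expectedness. The protocol itself describes vasodilation (1.1) and skin rash and burning with topical nitrate/nitrite (3.2.2). An event absent from the brochure could still follow a known pattern.
- **Safeguards that do not depend on causality.** All SAEs go to the sponsor within 24 hours regardless of causality (7.4.1, 7.6.2) and to the IRB/IEC (7.6.3). The DMC reviews safety data generally (11.7). The sponsor and authorities keep a general power to suspend (7.13). All adverse events are tabulated by treatment (9.5.4), so the randomized comparison does not need individual causality ratings.
- **An unseen document.** Section 7.4.1 leaves the detail of expedited reporting to a Safety/Medical Monitoring Plan, which may narrow the gap.

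The CRO Medical Monitor's final say on causality helps less. Section 7.4.3 gives that monitor no different criteria, and Sections 7.4.1 and 7.4.3 base the Related category on the investigator's rating.

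A reader might infer that a site must rate a new reaction Not Related. The documents do not support that: the Not Related definition does not fit the worked case either, nothing directs the event there, and a related grade chosen by judgment is equally open. A reader might also infer that a new serious reaction would go undetected, or that no event could be both unexpected and related. The safeguards above and the severity/frequency route rule out both.

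**Conclusion.** The concern holds in limited form, as a should-fix. As worded, a reaction new in nature meets no causality grade when another cause is unlikely or merely possible (8 of 8 combinations), and it can be rated related only if every other cause is excluded. What is at risk is inconsistent or falsely Not Related labelling, with its effect on the four uses of the label: expedited and SUSAR classification, the Section 7.13 trigger, SAE reports after follow-up, and the Related category in the tables. Detection and first reporting of an SAE within the reporting window are not at risk.

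This rests on a literal reading of the four definitions, on the five assumed levels for another cause, and on the event truly lacking a known pattern. How often such events would occur, and how sites would rate them, cannot be derived from the documents.

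**What to change.** In Section 7.4.3:

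1. Probably Related: drop the known-effect condition. Keep reasonable timing, improvement on withdrawal where it can be assessed, and another cause being unlikely.
2. Possibly Related: drop the known-pattern condition. Keep reasonable timing and the possibility of another cause.
3. Say that a known pattern supports either rating but is not required.
4. Say that any event not meeting Not Related is rated at least Possibly Related. Since the relaxed Possibly wording would overlap with Not Related when another cause is most likely, also say that Not Related applies where its own terms are met.

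On the same 20 combinations without a known pattern, this gives 3 + 8 + 1 = 12 related, 8 Not Related and 0 without a grade. Align the Safety/Medical Monitoring Plan and the eCRF guidance so that sites, the medical monitor and the reporting process use the same wording.

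The cost is a few words in the protocol and the matching guidance, with somewhat more adverse events rated related and a few more expedited reports. Sample size, endpoints, visits and treatment do not change.

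### The protocol ties relatedness to the Investigator's rating but gives the CRO Medical Monitor the final say, with no rule for when they disagree

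*Combined protocol and SAP*

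**What the plan says.** Section 7.4.1 (Reportability) sets the rule for expedited reporting: "For expedited reporting purposes, SAEs assessed as Definitely Related, Probably Related or Possibly Related by the Investigator will be considered as" Related. Events that the Investigator rates Not Related fall on the other side. Section 7.4.3 repeats the rule for the statistical analysis: "For analysis purposes, AEs assessed as Definitely Related, Probably Related or Possibly Related by the Investigator will be considered as" Related.

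After the definitions of the four causality categories, Section 7.4.3 brings in a second assessor: "The CRO Medical Monitor will review the Investigator's assessment of causality and may agree or disagree". It adds "Both the Investigator's and CRO Medical Monitor's assessments will be recorded", and then "The CRO Medical Monitor will have the final say in determining the causality". That last sentence has no exception for expedited reporting or for analysis.

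Three other sections depend on causality without naming the assessor:

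- Section 7.6.1 has the Sponsor report SUSARs, meaning serious drug reactions that are unexpected.
- Section 7.13 speaks of "Review of serious, unexpected, and related AEs by the CRO Medical Monitor" and other bodies.
- Section 9.5.4 tabulates adverse events by relationship to study treatment, among other factors.

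Section 7.4.1 leaves process detail to a Safety/Medical Monitoring Plan, which is not among the documents.

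**The concern.** Two rules apply to the same event. One makes the Investigator's rating decisive for two named purposes. The other makes the CRO Medical Monitor's rating decisive without limit. They agree as long as the assessors agree. They contradict each other exactly when a rule is needed.

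The direction of most concern is a serious, unexpected event that the site considers related and the monitor does not. Whether regulators receive it as a SUSAR would depend on which sentence the safety staff apply, and staff in different regions could apply different ones. The same event could be tabulated as related or as not related. The opposite case, in which the monitor upgrades an event that the Investigator rated Not Related, is equally unresolved.

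**Working it through.** The plan has no figure to reproduce here. The check sets the provisions side by side.

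**Step 1: which disagreements matter.** Each assessor has four categories, and three of them collapse to Related.

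- Possible rating pairs: 4 × 4 = 16.
- Pairs with both assessors on the same side: 3 × 3 (both Related) + 1 × 1 (both Not Related) = 10.
- Pairs on opposite sides: 3 × 1 (Investigator related, monitor not) + 1 × 3 (the reverse) = 6.

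Of the 16 − 4 = 12 pairs in which the ratings differ, 6 therefore change nothing: they are disagreements among Definitely, Probably and Possibly. The other 6 cross the line. These are counts of possible pairs, not frequencies.

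**Step 2: the two readings.** Reading A holds that the purpose-specific sentences in 7.4.1 and 7.4.3 govern. Reading B holds that the final-say sentence governs.

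| Investigator | CRO Medical Monitor | Reading A | Reading B |
|---|---|---|---|
| Related | Related | Related | Related |
| Related | Not Related | Related | Not Related |
| Not Related | Related | Not Related | Related |
| Not Related | Not Related | Not Related | Not Related |

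The readings differ in the two discordant rows and nowhere else.

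**Step 3: what follows in row two, for an SAE.**

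- *SUSAR reporting (7.6.1).* SUSAR status needs a causal link and unexpectedness. An expected event is unaffected. An unexpected one is reportable under A and could fall outside the definition under B.
- *Relationship table (9.5.4).* The event sits in the related column under A and in the not-related column under B.
- *Safety review (7.13).* The section refers to related events without saying who decides, so the same event is within its wording under A and outside it under B.

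**Step 4: what does not depend on the reading.** All SAEs go to the Sponsor whatever the causality (7.4.1, 7.6.2). SAEs go to the IRB/IEC under its own requirements (7.6.3). Both ratings are kept (7.4.3). All AEs and SAEs are listed and are also summarised by treatment received (9.5.4). The DMC reviews participant safety data without restriction to related events (11.7).

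**Step 5: is precedence stated anywhere?** Sections 7.4.1, 7.4.3, 7.6.1, 7.13, 9.5.4 and 11.7 contain no such statement.

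**The case against.** The strongest reply is that a specific rule outranks a general one. The only sentence written for expedited reporting, in 7.4.1, names the Investigator, and so does the sentence written for analysis. Read that way, nothing is downgraded out of SUSAR reporting and the tables are unaffected. This is a reasonable reading. It stands to the extent that a reader should not infer that the plan, as written, removes site-rated related events from SUSAR reporting. That happens on one reading only. But the protocol does not state the priority, and the final-say sentence plainly supports the other reading.

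A reader might also infer that the monitor controls a stopping trigger. The documents do not support this. Section 7.13 sets no count or threshold for these events. Its wording is discretionary, and it names the DSMB, the IRB and regulators alongside the monitor. Being listed first gives the monitor no priority.

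Nor do the documents support the inference that one person can make a site's signal disappear. The provisions in Step 4 keep the event visible. They do not, however, decide whether the Sponsor files a SUSAR report. The DMC meets at least biannually and after 1,000 participants complete follow-up, so its review is not a substitute for expedited reporting.

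Finally, the Safety/Medical Monitoring Plan may settle the matter. That cannot be checked here, and the protocol text would still conflict with itself.

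**Conclusion.** The contradiction is real and should be corrected. Two stated rules give opposite answers whenever the assessors fall on different sides of the Related/Not Related line, and no section sets precedence. The consequence is conditional. If the final-say sentence governs, an unexpected SAE that the Investigator rates related could miss SUSAR reporting and change column in the relationship table. If the purpose-specific sentences govern, it does neither.

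The number of events affected cannot be estimated. The documents give no rate of disagreement between assessors and no expected number of related SAEs. The nearest figure is in Section 1.5.2: no SAEs related to the spray were reported among 103 treated participants in the earlier prevention trial. That is too little to size the problem. Any count would also have to be limited to unexpected events before it applied to SUSARs. The primary efficacy analysis is not affected.

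The conclusion rests on the protocol text alone and assumes that no precedence rule in the Safety/Medical Monitoring Plan overrides it.

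**What to change.** Delete the final-say sentence from Section 7.4.3 and amend both 7.4.1 and 7.4.3 to state:

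- *The Investigator's and the CRO Medical Monitor's causality ratings are both recorded.*
- *For expedited reporting, an event is Related if either of them rates it Definitely, Probably or Possibly Related. The monitor's rating does not downgrade the Investigator's.*
- *The tables in Section 9.5.4 use the Investigator's rating, and events on which the two differ across the Related/Not Related line are listed.*

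Section 7.4.1 has to change as well. It now relies on the Investigator alone, so it would contradict the new rule for any event that the monitor upgrades. Section 7.13 must be reconciled with 7.4.3 so that it says whose assessment defines a related event there. Section 7.6.1 should point to the amended rule, and the Safety/Medical Monitoring Plan should be aligned with it.

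The change needs no new data, because both ratings are already collected. The cost is a short text amendment and possibly a few more expedited reports.
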